#### Home Monitoring for arrythmias

Telemetry tracings from the implantable monitor will be reviewed monthly or whenever an event occurs and/or a patient transmits data due to symptoms via remote assistance.

Default transmission is data sent daily between 1:00AM and 2:00AM regardless of events. If there is a problem with transmission the device will alert the physician within 24 hours and this will help to maintain compliance of transmission.

If no events occur the device will be interrogated prior to explantation at the end of the 6 month monitoring period.

The study investigators will be responsible for telemetry review. The patient's treating cardiologist will be notified of events of clinical significance. Treatment of the arrhythmias will be based on current clinical guideline recommendations for bradycardia and VA. Clinical follow up will occur via standard of care clinical visits.

SCD is defined as sudden and unexpected death within 1 hour of cardiac symptoms in the absence of progressive cardiac deterioration, unexpected death during sleep, or unexpected death within 24 hours after last being seen alive. Study participants who experience SCD while monitored and are successfully resuscitated after life-threatening VA will receive an implantable cardioverter defibrillator based on current clinical guidelines. These and other arrhythmic events recorded by the implantable monitor, or SCD that cannot be successfully resuscitated, will be considered events of interest and NOT adverse events, as these are not a consequence of monitoring via the implantable device.

At the end of the 6 month monitoring period, the device will be explanted. Participants will be offered the choice to retain the device until battery end of life if clinically indicated. However, patients who opt to continue monitoring will be informed that their insurance

company will be billed for clinically indicated monitoring and explantation outside the study time frame.

For any patients who expire during the study monitoring period, the terminal rhythm of participants who die will be reviewed remotely via the Biotronik website irrespective of whether the monitor can be retrieved. Patients will be informed of this possibility during the consent process.

For stage III patients with existing ICD or pacemakers, rhythm monitoring will be obtained from the device over a 6 month timeframe and may be retrospective if applicable.

Patients with existing implantable cardiac devices will undergo a device interrogation at enrollment and at the end of the 6 month monitoring period. If available, records from interim routine and unscheduled clinical device interrogations during the 6 month monitoring period be requested for review by the investigators.

Routine clinical follow up will be continued including clinically indicated ECHOs, ECGs,

I imeline for testing:		
Tests		
	At baseline (clinical echo within 6 months of enrollment date) and scheduled as clinically	
ECHO- TTE	indicated	
Biopsy or technetium pyrophosphate scintigraphy	As clinically indicated, inclusion criteria for the study	
pyrophosphate schutgraphy		
	Clinically indicated at baseline (within 6 months of	
EKG	enrollment) and when clinically indicated	
MRI with T1	When clinically indicated	
Cardiopulmonary exercise		
test	When clinically indicated	
Biomonitor 3	Monitored with a clinically significant event	
NT proBNP	When clinically indicated, inclusion criteria for the study based on clinically indicated testing	
	When clinically indicated, inclusion criteria for the	
Troponin T	study based on clinically indicated testing	
Labs: CBC, Basic Metabolic		
Panel, Mg	When clinically indicated	
Urine pregnancy	At baseline for women of child bearing potential	

Timeline for testing:

and blood work.

An insertable monitor may be removed emergently at the investigator's discretion at any time subsequent to an implant procedure. Reasons for removal include, but are not limited to: patient death; loss of sensing; inability to program/interrogate the inserted monitor; infection, EOS (normal or premature); or other reason(s). Complications related to other portions of the insertable monitor system may also result in insertable monitor removal.

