#### 1.4 Study Rationale and Risk/Benefits

#### 1.4.1 Study Rationale

TTR-wt cardiomyopathy has been considered a life limiting, if indolent, and untreatable cause of heart failure in older individuals. For this reason, clinicians have hesitated to treat potentially life threatening arrhythmias, or to consider implantation of cardiac devices (PPM or ICD) which may improve symptoms and impact mortality. The recent availability of disease modifying therapies ushers in a new era of treatment strategies which improve both mortality and morbidity. The goal of the study is to identify patients who would also benefit from treatment of arrhythmias, and who might otherwise have succumbed to complications from arrhythmias, including stroke, sudden cardiac death, or injury from syncope due to bradycardia.

Implantable loop recorders have been used successfully to monitor for arrhythmia burden and to identify causes of cryptogenic syncope and stroke in patients with cardiovascular disease (19,20). The devices can be implanted at low risk and with local anaesthesia and can be inserted in an office setting, and remaining in situ for up to 3 years to permit long term monitoring (21). The device are explanted at the time of battery expiration. Miniaturized implantable loop recorders have been used to document mechanisms of sudden death in late stage AL amyloidosis but have not been routinely utilized especially in TTR-wt (8). Given the perceived high risk for arrhythmias and the lack of robust data on arrhythmia burden, amyloid cardiomyopathy would seem an ideal population to monitor with implantable long-term loop recorders.

An observation from the recently published Transthyretin Amyloidosis Cardiomyopathy Clinical Trial (ATTR-ACT) was the subgroup analysis suggesting greater benefit in less severe heart failure (17,22). Arrhythmia risk (AF, heart block, and cardiac arrest) might be different in patients with earlier stages of the disease, and if treatment with tafamidis might prevent further progression of conduction system disease and arrhythmia burden. The current study proposed is a pilot study and will not be powered to ascertain the effects of tafamidis on arrhythmia burden in different stages of disease, but observations from the study will provide preliminary data for future and necessary prospective monitoring studies.

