## 2 Study Objectives

Listed below are the specific aims/objectives for this study.

**Specific Aim 1**: Burden of conduction system disease and arrhythmias, specifically sinus node dysfunction, high grade heart block, and AF and VA, which will identify those who might benefit from a PPM or ICD

**Specific Aim 2**: Mechanism of SCD (asystole, pulseless electrical activity, or sustained VA) and whether this is different in early vs. late stage amyloidosis.

**Specific Aim 3**: Risk factors for SCA and more specifically whether bradycardia or VA predict SCD, or whether there are imaging or clinical characteristics that predict SCA **Specific Aim 4**: Utility of long term ECG monitoring in TTR-wt cardiomyopathy

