#### 3.2 Primary Study Endpoints

1. Sudden cardiac death (including resuscitated cardiac arrest).

2. Syncope due to heart block or sinus node dysfunction requiring pacemaker

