#### 4.5 Description

Biomonitor 3 is a programmable, subcutaneous insertable monitor able to record subcutaneous ECGs (sECGs) and other physiological parameters.

The Biomonitor 3 is designed to automatically record the occurrence of arrhythmias in a patient. Arrhythmia may be classified as atrial fibrillation (AF), bradyarrhythmia, asystole, sudden rate drop, or high ventricular rate. In addition, the Biomonitor 3 can be activated by the patient to record cardiac rhythm during symptomatic episodes.

The Biomonitor 3 system consists of three main components:

 Biomonitor 3 insertable cardiac monitor - The Biomonitor 3 is a small, leadless device that is typically inserted under the skin, in the chest. The device uses two electrodes on the body of the device to continuously monitor the patient's subcutaneous ECG. The device memory can store up to 30 min of subcutaneous ECG (sECG) recordings from automatically detected arrhythmias and up to 30 min of sECG recordings from patient-triggered episodes. When a patient experiences symptoms, the sECG recordings can be manually triggered by placing the Remote Assistant III over the Biomonitor 3. The insertable monitor is provided preloaded in an insertion tool. An incision tool is also provided.

Note - The Biomonitor 3 subcutaneous ECG may differ from a surface ECG due to differences in electrode separation and device placement in the body. Biomonitor 3 detects a subcutaneous ECG from a pair of electrodes. These signals are filtered in two different ways. For detection of QRS complexes, the signals are filtered with a passband of 10-40 Hz in order to suppress T-waves, artifacts, and baseline drift at low frequencies, and myoptentials and EMI at high frequencies. The resulting signal is appropriate for QRS detection as other components of the signal have been suppressed. This signal naturally does not have a typical ECG morphology due to the bandpass. For waveform display (real-time streaming sECG with the physician's programmer and snapshots for review by the physician), a different passband is 0.5 – 40 Hz, which is designed to retain morphological features of a typical ECG while still rejecting large low frequency artifacts and baseline drift.

- 2. BIOTRONIK Renamic / ICS 3000 Programmer The programmer is used to set up the Biomonitor 3 to detect arrhythmias. It also allows you to view, save, or print the stored information.

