#### **Primary Hypothesis:**

The primary hypothesis that arrhythmogenesis and SCD risk in this population is influenced by amyloid cardiomyopathy stage rather than reduced left ventricular ejection fraction, which is often a marker of late disease and increased mortality due to heart failure, and that SCD due to asystole, rather than VA which could be treated with ICD. Conduction system disease causing heart block, atrial arrhythmias and VA leading to SCD may occur earlier in the disease process and treatment of AF, VA, and heart block could improve both morbidity and mortality.

A Student's t-test will be used to compare differences in arrhythmia burden between the patients in the two groups (early stage I-II vs stage III either with any implanted cardiac device).

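### Two of the three limbs of the sudden cardiac death definition require no cardiac cause, and nothing in the plan removes a death with a documented non-cardiac cause from primary endpoint 1

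*Combined protocol and SAP*

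**What the plan says.** The definition is in section 5, under home monitoring. The first limb reads: "SCD is defined as sudden and unexpected death within 1 hour of cardiac symptoms in the absence of progressive cardiac deterioration". The second and third, joined to it by a simple *or*, are "unexpected death during sleep, or unexpected death within 24 hours after last being seen alive".

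Section 3.2 makes sudden cardiac death, with resuscitated arrest included, the first primary endpoint. Aim 2 in section 2 concerns the "Mechanism of SCD (asystole, pulseless electrical activity, or sustained VA) and whether this is different in early vs. late stage amyloidosis".

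The only step described after a death is in section 5: "the terminal rhythm of participants who die will be reviewed remotely via the Biotronik website irrespective of whether the monitor can be retrieved". No rule says how that review changes the classification of the death. Section 5 makes the study investigators responsible for telemetry review, and no adjudication of cause of death is described.

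**The concern.** A cardiac endpoint should not be met by a death known to have another cause. Here the cardiac element belongs to the first limb alone. The sleep and 24-hour limbs ask only that the death be unexpected and occur in a given circumstance or time window.

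The plan itself foresees other fatal events. Section 1.4.1 says patients might succumb to "complications from arrhythmias, including stroke, sudden cardiac death, or injury from syncope due to bradycardia", which lists stroke separately from SCD.

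A non-cardiac death that meets the second or third limb would enter primary endpoint 1. It would also enter Aim 2, which has no place for it: the mechanism must be asystole, pulseless electrical activity or sustained ventricular arrhythmia. In a 50-patient pilot with few deaths, a single such entry matters to the count and to the mechanism table.

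**Working it through.** The plan states no SCD rate, power or target event count, so there is no figure to reproduce. The check is of the wording first, then of scale.

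**Wording**

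- Limb 1: sudden and unexpected, within one hour of cardiac symptoms, no progressive cardiac decline. Cardiac element present.
- Limb 2: unexpected, during sleep. No cardiac element.
- Limb 3: unexpected, within 24 hours of last being seen alive. No cardiac element.

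Suppose the limb 1 qualifiers were read across all three limbs. A stroke, embolic or bleeding death can be sudden and is not progressive cardiac deterioration, so it would still not be excluded.

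**Other places that might supply the exclusion**

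- Section 3.2 names the endpoint without a cause rule.
- Section 3.3 tracks all-cause mortality with attention to heart failure and bradycardic deaths, but gives no classification rule.
- Section 4.2, exclusion 7, removes patients with known competing life-threatening disease at entry. It does not reach acute events during follow-up.
- Section 6.2 has no rule on cause of death.
- Section 8.2 names neither autopsy reports nor death certificates among the source documents.

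**Scale**

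Inputs: four-year survival of 57%, 42% and 18% for stages I, II and III (section 1.4.1); 25 patients in stage I or II and 25 in stage III (section 4). A constant hazard is assumed, so six-month death risk = 1 − S^(0.5/4) = 1 − S^(1/8).

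- Stage I: 1 − 0.57^(1/8) = 6.8%; 25 patients give 1.70 deaths.
- Stage II: 1 − 0.42^(1/8) = 10.3%; 25 patients give 2.57 deaths.
- Stage III: 1 − 0.18^(1/8) = 19.3%; 25 patients give 4.82 deaths.

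Total deaths: 1.70 + 4.82 = 6.52 if the early group is all stage I, and 2.57 + 4.82 = 7.39 if it is all stage II.

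The share of deaths that are unexpected, non-cardiac and within limb 2 or 3 is not in the documents. For an assumed share q, expected miscounts are m = q × deaths, and the chance of at least one is 1 − (1 − m/50)^50.

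| q | Expected miscounts | Chance of at least one |
|---|---|---|
| 2% | 0.13 to 0.15 | 12% to 14% |
| 5% | 0.33 to 0.37 | 28% to 31% |
| 10% | 0.65 to 0.74 | 48% to 53% |
| 20% | 1.30 to 1.48 | 73% to 78% |

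One false event added to x true SCDs makes up 1/(x + 1) of the count: 50% for x = 1, 25% for x = 3, 17% for x = 5. These values of x are illustrative.

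**The case against.** The strongest reply is that this is a minor wording matter in a descriptive pilot. The label itself says cardiac, section 1.4.1 separates stroke from SCD, and a sensible investigator would not call a documented stroke an SCD. That may well be what happens, but it would be an unwritten decision that departs from the stated definition.

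It is also fair that the death count may be too high. Exclusion 7 removes some competing mortality, section 1.1 says newer therapies improve survival, and section 5 allows a retrospective six-month window for stage III patients with existing devices. A patient enrolled after such a window cannot have died in it. These points lower the expected number; they do not supply the missing exclusion.

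A reader might go further and infer that miscounted deaths would be recorded as asystole, would fall mainly in stage III, and would so favour the primary hypothesis, which refers to "SCD due to asystole, rather than VA which could be treated with ICD". The documents do not support this:

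- **Mechanism.** The recorder's list ("Arrhythmia may be classified as atrial fibrillation (AF), bradyarrhythmia, asystole, sudden rate drop, or high ventricular rate") includes asystole and not pulseless electrical activity, which makes the inference tempting. But Aim 2 allows pulseless electrical activity, section 4.1 admits patients with pacemakers or defibrillators, and no rule maps terminal rhythm to mechanism.
- **Stage.** Stage III supplies 65% to 74% of the expected deaths (4.82/7.39 to 4.82/6.52). Carrying that over to non-cardiac deaths assumes the same non-cardiac share in every stage. Section 1.4.1 links short survival in advanced disease to heart failure, so the share could be lower there.
- **Hypothesis.** Section 6.2 says stage influences SCD risk, not that SCD is more frequent in stage III, and it adds that ventricular arrhythmia leading to SCD may come earlier in the disease.
- **Test.** The only planned test is a t-test on arrhythmia burden. No planned test uses SCD counts.

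**Conclusion.** The point holds on the wording: the rule for primary endpoint 1 is over-inclusive, and Aim 2 has no category for the deaths it wrongly admits. The likely number is small, about 0.1 to 1.5 deaths. That range rests on a constant hazard, on survival figures that may overstate deaths in this cohort, and on an assumed 2% to 20% share of unexpected non-cardiac deaths. The consequence is descriptive: with a handful of true SCDs, one miscount noticeably changes the reported count and the mechanism split. No claim about the direction of bias, by stage or by mechanism, is warranted.

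**What to change.** In section 5, add that a death with a non-cardiac cause documented in the available records is not SCD under any limb. For the remaining deaths that meet the sleep or 24-hour limb:

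- Count as SCD those with cardiac evidence, for example a recorded terminal arrhythmia. State beforehand which recordings qualify and who decides.
- Label those with no cause information *SCD, cause undetermined*, so that an undocumented death does not become a definite SCD by default.

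In section 6.2, report endpoint 1 and the Aim 2 mechanism table with and without the undetermined deaths, and add a *mechanism undetermined* category to the table. If autopsy reports or death certificates are to be used, name them in section 8.2; otherwise limit the rule to the electronic medical record and the transmitted rhythm.

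The cost is a few sentences. The SCD count may fall slightly, and two counts are reported instead of one.

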#### **Unanticipated Adverse Device Effect (UADE)**

A UADE is any serious adverse effect on health or safety or any life-threatening problem or death caused by, or associated with, implantation of the device, or any other unanticipated serious problem associated with a device that relates to the rights, safety, or welfare of subjects.

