#### Adverse Effect (Event)

Any infection at the site of the implantable device, excessive unstoppable bleeding or development of a hematoma requiring evacuation, or malfunction of the FDA approved device in a subject involved in this clinical trial. Malfunction of the device includes but is not limited loss of sensing; inability to program/interrogate the inserted monitor; or premature EOS. Complications related to other portions of the insertable monitor system may also result in insertable monitor removal.

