#### Unanticipated Problems Involving Risk to Subjects or Others (UPIRTSO)

Any unanticipated problem or adverse event that meets all of the following three criteria:

• Serious: Serious problems or events that results in significant harm, (which may be physical, psychological, financial, social, economic, or legal) or increased risk for the subject or others (including individuals who are not research subjects). These include: (1) death; (2) life threatening adverse experience; (3) hospitalization - inpatient, new, or prolonged; (4) disability/incapacity - persistent or significant; (5) birth defect/anomaly; (6) breach of confidentiality and (7) other problems, events, or new information (i.e. publications, DSMB reports, interim findings, product labeling change) that in the opinion of the local investigator may adversely affect the rights, safety, or welfare of the subjects or others, or substantially compromise the research data, **AND** 

- Unanticipated: (i.e. unexpected) problems or events are those that are not already described as potential risks in the protocol, consent document, not listed in the Investigator's Brochure, or not part of an underlying disease. A problem or event is "unanticipated" when it was unforeseeable at the time of its occurrence. A problem or event is "unanticipated" when it occurs at an increased frequency or at an increased severity than expected, **AND**
- Related: A problem or event is "related" if it is possibly related to the research procedures.

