#### 7.2 Recording of Adverse Events

Study subjects will be routinely questioned about adverse effects at study visits. Information on all adverse events will be recorded immediately in the source document, and also in the appropriate adverse event section of the case report form (CRF). All clearly related signs, symptoms, and abnormal physical exam of the implant site will be recorded in the source document.

All adverse events occurring during the study period will be recorded. All observed or volunteered adverse effects (serious or non-serious) will be recorded in the subjects' case history. For all adverse effects sufficient information will be pursued and or obtained as to permit; an adequate determination of the outcome, an assessment of the casual relationship between the adverse effect and the device. The clinical course of each event will be followed until resolution, stabilization, or until it has been ultimately determined that the study treatment or participation is not the probable cause.

The only laboratory values that will prompt an investigation would be an elevated leukocytosis IN ADDITION to a physical inspection of the implanted site. If the implanted site is erythematous, hot, swollen, or there is drainage from the skin would further steps need to be taken to possibly extract the device. Positive blood cultures would indicate the necessity of a physical exam and inspection of the implant site.

A form will be created for capturing information related to adverse events and submitted to the IRB.

Adverse Event CRF:

- Subject Study Number/Identifier
- Device information (model and serial number)
- Date of event onset
- Description of the event
- Indicate if device needed to be explanted
- Subject current status, or if the event was resolved
- Principal Investigator assessment of if the event was serious and justification for

determination

• Principal Investigator assessment of causality and relationship to study treatment.

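### Section 5 rules in advance that no sudden cardiac death or recorded arrhythmia is an adverse event; it allows no exception and is not reconciled with the safety definitions in section 7

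*Combined protocol and SAP*

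**What the plan says.** Section 5, Home Monitoring for arrythmias, covers participants resuscitated after a life-threatening ventricular arrhythmia. It then groups them with any further arrhythmia that the monitor picks up and with fatal SCD, and rules that the whole group "will be considered events of interest and NOT adverse events, as these are not a consequence of monitoring via the implantable device". It states no exception. SCD, with resuscitated arrest included, is also the first primary endpoint in section 3.2.

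Section 7 defines safety events separately:

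- **UADE (7.1).** The definition takes in "any life-threatening problem or death caused by, or associated with, implantation of the device". It makes no carve-out for SCD. Section 7.3 has the sponsor-investigator review documented UADEs promptly and report as necessary to FDA within 10 working days and to the IRB within 5.
- **Adverse event (7.1).** Device malfunction is an adverse event in its own right: "Malfunction of the device includes but is not limited loss of sensing; inability to program/interrogate the inserted monitor". The list is open, but it does not name a failed transmission or an alert that was not acted on.
- **UPIRTSO (7.1).** This has its own tests of seriousness (death is named), unexpectedness and possible relation to the research procedures.
- **Recording (7.2).** A causal assessment is required for adverse effects, and the Adverse Event CRF carries a seriousness item and a "Principal Investigator assessment of causality and relationship to study treatment".

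Section 5 also has the terminal rhythm reviewed remotely for every death in the monitoring period.

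**The concern.** An endpoint event can be counted once, as an endpoint, and still be asked whether the study contributed to it. Section 5 answers that second question by rule. In a study whose only intervention is a monitor and the process of reading it, the harm most worth looking for is an event that follows a failure of the monitoring. Examples are a device that stopped sensing, a transmitter that was off, or an alert that nobody reviewed in time. Read as written, the rule classes such a death as unrelated without anyone having to look.

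Two things follow. First, safety reporting depends on which section a site reads first, because nothing says which prevails. Second, Aim 4 asks about the utility of long-term monitoring. If nobody records whether the system was sensing, transmitting and being read at the time of each SCD, it is harder to tell monitoring that did not help from monitoring that was not working.

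**Working it through.** The plan states no figure on this point, so the check sets the passages side by side and follows four kinds of event through them.

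1. **SCD or resuscitated arrest with no recognised device problem.** Under section 5 it is not an adverse event. Both causality steps in 7.2 (the narrative requirement and the CRF item) apply to adverse effects or sit on the Adverse Event CRF, so the event does not reach them.

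2. **Death associated with the insertion.** Under 7.1 this is a UADE, and 7.3 provides for its review. If the death is also an SCD, section 5 says it is not an adverse event. The two statements conflict directly. Section 5's reason speaks of monitoring, not insertion, which favours 7.1, but its classification covers fatal SCD without qualification.

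3. **SCD after a malfunction such as loss of sensing.** The malfunction is an adverse event under 7.1 and gets a form with a causality item. The death stays excluded by section 5, and nothing requires the two to be linked.

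4. **SCD after a failed transmission or an alert not acted on.** The malfunction definition does not name this. The failure is foreseeable from the protocol itself: section 4.7 lists four reasons why updated data may be unavailable, section 4.5 (Communication Loss) describes loss lasting up to 90 days before the patient is deactivated, and section 5 makes the investigators responsible for telemetry review. No step checks an SCD against any of these.

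The next question is whether the other routes make up for the exclusion.

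- **UADE.** A death qualifies only once someone finds it caused by or associated with implantation, and 7.3 reviews only documented UADEs. No step asks the question for an SCD.
- **Malfunction.** This assesses the malfunction, not the death. Reporting is also unclear: the narrative in 1.4.2 names malfunction as a risk, the bulleted list there omits it, and section 7 says expected events from 1.4.2 will not be reported.
- **UPIRTSO.** An event need not be an adverse event to be tested here. But the unexpectedness criterion screens out what belongs to the underlying disease, and section 1.1 describes SCD as a feature of cardiac amyloidosis.
- **Terminal rhythm review.** This establishes the rhythm, not whether the system was working. It relies on the remote website, so it may have little to show when transmission had failed.

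Each route is open, and each depends on a suspicion of relatedness that section 5 has already ruled out.

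**The case against.** The strongest case on the other side is that this is a drafting gap in a low-risk study. The device is approved and used as approved, standard care is unchanged, SCD is an expected outcome and a primary endpoint, and section 7 has several safety routes that do not depend on section 5. Most of that stands, and it rules out several stronger readings.

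- A reader might infer that a device-linked death never gets a causality assessment. The documents do not support that. Death associated with implantation is a UADE subject to review, a malfunction is an adverse event, and a possibly related serious problem can be tested as a UPIRTSO.
- A reader might infer that seriousness and causality are assessed only on the Adverse Event CRF. The UPIRTSO definition has its own tests, and the 7.2 narrative requires a causal assessment of adverse effects.
- A reader might infer that an arrhythmia during the insertion would be recorded by the implant and so classed away. Nothing says the device records during its own insertion, and a life-threatening problem associated with implantation falls under the UADE definition anyway.
- A reader might convert the four-year survival in section 1.4.1 (57%, 42% and 18% for stages I, II and III) into a count of affected deaths. With a constant hazard, six-month mortality is 1 − S^(0.5/4): 1 − 0.57^0.125 = 6.8%, 1 − 0.42^0.125 = 10.3% and 1 − 0.18^0.125 = 19.3%. In 25 + 25 patients that gives 25 × 0.193 + 25 × (0.068 to 0.103), or about 6.5 to 7.4 deaths. If 25 to 50% were sudden, an assumption with no source in the documents, that is 1.6 to 3.7 SCDs. This counts all SCDs, not device-linked ones, so it does not measure harm. It also ignores patients followed through an existing pacemaker or ICD, the life-expectancy exclusion in 4.2 and the newer therapies described in 1.1.
- The Aim 4 argument is limited too. Transmission facts should already be in the monitoring record and could be retrieved whatever the event is called. What is missing is any instruction to collect them for each death.

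The objection does not explain why causality is declared in advance, and it does not say which section prevails.

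**Conclusion.** The point holds as a conflict and a missing step. Section 5 presumes that every SCD and recorded arrhythmia is unrelated to the monitoring, with no case-by-case exception. That conflicts with the UADE definition, sits unreconciled with the malfunction and UPIRTSO definitions, and keeps these events from reaching the 7.2 causality items as events in their own right. No step requires an SCD or resuscitated arrest to be screened for a device, transmission, alert or insertion contribution. The gap is clearest for transmission and alert failure and weakest for insertion.

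The size of the harm cannot be stated: the number of device-linked SCDs is unknown and may be zero. The conclusion rests on the wording of sections 5 and 7 and assumes that a site applies section 5 as written. It needs no event rate. This should be corrected, but it does not undermine the study.

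**What to change.** In section 5, delete the closing clause that gives non-causality as the reason. State instead that these events are analysed as study endpoints and are not tallied as adverse events unless the investigator judges them possibly related to the insertion, the device or the monitoring process, in which case section 7 applies.

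For each SCD and resuscitated arrest, complete the seriousness and causality items already on the Adverse Event CRF. Add three facts from the monitoring record: whether the device was sensing, when the last successful transmission occurred, and when any alert was reviewed. Events judged possibly related then go through 7.3.

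The screen need not extend to syncope, which the section 5 sentence does not name.

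The cost is a change of protocol wording and a short addition to an existing form. The downside is a few extra causality assessments and possibly an occasional additional IRB report. Endpoint events otherwise stay out of the adverse event tally, and no clinical rule changes.
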